	To assess the time to progression ratio after a second SABR course, i.e. the ratio of the TTP2 measured from the time of first progression to the time of progression after the second SABR course, over the TTP1 measured from the time of inclusion in the trial to the time of first progression, in patients with lung cancer and sarcoma who received a second SABR course.
	 To assess the objective response rate at 6 weeks after the second SABR course, using RECIST v1.1, in the case of an oligoprogression and continuation of Atezolizumab at the time of progression in patients with lung cancer and sarcoma.
	- To compare the modification of the size of the lesion which received the second SABR session versus the lesion that is not (abscopal effect) in patients with lung cancer and sarcoma.
Exploratory Objectives	- To evaluate the functional imaging changes using FDG PET/CT and tumour growth rates
	 To evaluate the systemic immunologic anti-tumour response based on the sequential tumour biopsies and immunomonitoring on peripheral blood samples.
Methodology	Open-label, non-comparative, phase II clinical trial conducted in four cohorts of patients:
	- Cohort 1: metastatic colorectal cancer (closed to inclusions)
	- Cohort 2: metastatic non-small lung cancer (closed to inclusions)
	- Cohort 3: metastatic renal cell carcinoma (closed to inclusions)
	- Cohort 4: metastatic sarcoma (closed to inclusions)
	In addition, cohorts 2 and 4 will also serve to address the impact of a second SABR course on possible oligoprogressive lesion(s), defined as \leq 3 extracranial sites of progressive disease, and continuation of atezolizumab.
	Patients will receive:
	- atezolizumab at a dose of 1200 mg every 3 weeks, until disease progression or unacceptable toxicity, and
	- stereotactic ablative radiation therapy, with the second cycle of atezolizumab (week 4) using 6MV photons or other energies with standard field encompassing tumour. Hypofractionated SABR will be delivered at a dose of 45 Gy in 3 fractions of 15 Gy (equivalent biologic dose (BED) > 80 Gy). The recommended fractionation is 45 Gy (3 fractions of 15 Gy) but shall be adapted upon normal tissue tolerance constraints. Total duration of radiotherapy must not exceed eight days and a window of \pm 3 days allowed to start the treatment.
	- in patients with lung cancer and sarcoma cancer who progress after SABR +

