4 SELECTION OF PATIENTS

4.1 Inclusion criteria

- 1. Patients must be 18 years of age or older.
- 2. Histologically or cytologically proven metastatic solid tumours including:
 - colorectal (CRC, Microsatellite instability negative and positive) in treatment failure as per the current standard recommendation (cohort closed to inclusions);
 - non-small cell lung cancer (NSCLC) pretreated by at least one line of treatment. Patients EGFR-mutant can be included only if they have been treated with, or developed toxicity with or refused to be treated with anti-EGFR therapy. Patients pretreated by anti-PD1, or anti-PDL1 therapeutic antibodies can be included only if they have received at least 4 months of treatment (cohort closed to inclusions);
 - renal cell carcinoma (RCC) pretreated by at least one line therapy by a tyrosin kinase inhibitor (cohort closed to inclusions);
 - metastatic sarcomas of any type (soft tissue, bone, GISTs) pretreated by at least one line of standard therapy; at least three lines of standard TKi must be given in patients with GISTs. No enrolment restriction to certain sarcoma subtypes/groups was decided given the relative rarity of this disease type and that immunotherapy efficacy in certain histological subtypes is only preliminary (cohort closed to inclusions).

3. Patients with at least:

- one measurable metastasis by RECIST 1.1 eligible for SABR in terms of dose constraints at organ at risk (refer to Appendix 1: Rules for SABR administration according to tumour location); distinct criteria apply regarding lung and liver metastases) and ≤ 4 cm, and
- one not treated measurable metastasis by RECIST 1.1. If all tumour sites are accessible to SABR, one of them will not be treated.

Metastase located within the proximal bronchial tree as defined in RTOG 0236 (refer to Appendix 1: Rules for SABR administration according to tumour location) or within the brain are not eligible for SABR treatment in the present study. However, it can be considered as a not treated evaluable metastase.

- 4. WHO performance status of 0-1
- 5. Evaluation by a radiation oncologist within 45 days prior to study registration, including imaging workup to document metastases (cf. description in assessment section)
- 6. Patients must have adequate organ function defined by the following laboratory results obtained within 28 days prior to the first study treatment:
 - Absolute neutrophil count of ≥ 1500/mm3;
 - Lymphocyte count ≥ 500 mm3;

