8.3 Data Analysis

8.3.1 General Considerations

- Statistical analysis for this study will be the responsibility of the Sponsor. For continuous variables, summary statistics will include number of patients, mean, standard deviation, median, interquartile range, minimum, and maximum. Categorical endpoints will be summarized using number of patients and frequency in %. Missing data will not be imputed.
- The interpretation of the study results will be the responsibility of the investigators, pharmacokineticist and statistician.
- Exploratory analyses of the data not described below will be conducted as deemed appropriate.

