8.3.2 Efficacy Analysis

Progression free survival (PFS) is defined as the time from treatment initiation to first documentation of tumour progression or to death, whatever the cause of death, whichever occurs first. Any patient that discontinues due to a reason other than progressive disease (for example, AE, patient/investigator decision) will have their time-to-event data either censored at

the follow-up visit if no progressive disease is found during this visit, or censored at the date of the last objective progression-free disease assessment if progressive disease is found at the follow-up visit. The progression will be assessed using RECIST v 1.1 and mRECIST.

Time to progression of non irradiated lesions is computed as the delay from enrollment to the first occurrence of progression outside of the irradiated field. Time to progression of irradiated lesions is computed as the delay from enrollment to the first occurrence of progression of irradiated lesions.

The disease Control Rate (DCR) will be defined as the sum of complete responses (CR), partial responses (PR) and stable disease (SD). The objective Response Rate (ORR) will be defined as the sum of complete responses (CR) and partial responses (PR).

The PFS, DCR, ORR and DOR will be computed by patient. In each cohort, response rates with exact 95% confidence intervals will be provided, and PFS and duration of response will be estimated using Kaplan-Meier survival method and presented with Rothman's 95% Confidence Intervals. Median follow-up will be estimated using inverse Kaplan-Meier method (Collet D., 1994). Secondary analysis will investigate the impact of the number of metastatic sites in 2 modalities (<5 and ≥5). A semi-parametric Cox model stratified on the cohort and adjusted for the number of metastasis will be developed.

The TTP ratio (TTPr) will be computed in all patients receiving a second SABR course, as the ratio of TTP2 over TTP1. Patients receiving a second SABR course without a documented progression 1 will not be included. Patients dying without documented second progressions will be counted as progressions at the date of death considering the very poor prognosis of those patients. Censored TTP2 will make the TTPr censored too. In this case, the Kaplan-Meier approach will be used to derive values of TTPr. For instance, rate of patients with TTPr greater than 1.5 will be computed, among other thresholds (1.33, 1.5, 2).

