CT and MRI are the best currently available and reproducible methods to measure target lesions selected for response assessment. Conventional CT and MRI should be performed with cuts of 5 mm or less in slice thickness contiguously. Spiral CT should be performed using a 5 mm contiguous reconstruction algorithm. This applies to the chest, abdomen and pelvis.

Ultrasound, endoscopy and laparoscopy should not be used to measure tumour lesions or evaluate tumour response. However, these techniques can be useful to supplement information from other techniques.

Tumour markers alone cannot be used to assess response. If markers are initially above the upper normal limit, they must normalise for a patient to be considered in complete clinical response.

Cytology and histology can be used to differentiate between PR and CR in rare cases (for example, residual lesions in tumour types such as germ cell tumours, where known residual benign tumours can remain).

Baseline Documentation of Target and Non-target Lesions

All measurable lesions up to a maximum of two lesions per organ and five lesions in total, representative of all involved organs should be identified as target lesions and will be recorded, measured and numbered at baseline. The longest diameter will be recorded, except for lymph nodes, which will be measured by their short axis. Target lesions should be selected on the basis of their size (lesions with the longest diameter) and their suitability for accurate repetitive measurements (either by imaging techniques or clinically).

The sum of diameters for all target lesions will be calculated and reported as the baseline sum of diameters. The baseline sum of diameter will be used as reference to further characterize the objective tumour response of the measurable dimension of the disease (Table 1.1).

Table 1.1: Evaluation of target lesions

Complete Response (CR)	Disappearance of all target lesions. Any pathological lymph nodes (whether target or non-target) must have a reduction in short axis to <10mm)
Partial Response (PR)	At least a 30% decrease in the sum of diameters of target lesions, taking as reference the baseline sum diameters

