Progression (PD)	At least a 20% increase in the sum of diameters of target lesions, taking as reference the smallest sum on study (this includes the baseline sum if that is the smallest on study). In addition to the relative increase of 20%, the sum must also demonstrate an absolute increase of at least 5 mm. (Note: The appearance of one or more new lesions is also considered progression.)
Stable Disease (SD)	Neither sufficient shrinkage to qualify for PR nor sufficient increase to qualify for PD, taking as reference the smallest sum diameters while on study.

All other lesions (or sites of disease) should be identified as non-target lesions and should also be recorded at baseline. Measurements are not required and these lesions should be followed as "present" or "absent" (Table 1.2).

Table 1.2.: Evaluation of non target lesions

Complete Response (CR)	Disappearance of all non-target lesions and normalisation of tumour marker level. All lymph nodes must be non-pathological in size (<10mm short axis)
Non-CR / Non-PD	Persistence of one or more non-target lesions and/or maintenance of tumour marker level above normal limits
Progression (PD)	Unequivocal progression (see comments below) of existing nontarget lesions. (Note: the appearance of one or more new lesions is also considered progression).
	Although a clear progression of non-target lesions only is exceptional, in such circumstances, the opinion of the treating physician should prevail and the progression status should be confirmed later by the review panel (or study chair).

In some circumstances it may be difficult to distinguish residual disease from normal tissue.

When the evaluation of complete response depends upon this determination, it is recommended that the residual lesion be investigated (fine needle aspirate/biopsy) before confirming the complete response status.

Evaluation of Best Response to Study Treatment

The best response to study treatment (Table 1.3) is the best response recorded from the start of treatment until disease progression or start of further anti-cancer treatment (taking as reference for progressive disease the smallest measurements recorded since the treatment started). In general, the patient's best response assignment will depend on the achievement of both measurements and confirmation criteria.

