Target lesions should be selected on the basis of their size (lesions with the longest diameter) and be representative of all involved organs, but in addition, should lend themselves to reproducible repeated measurements. It may be the case that, on occasion, the largest lesion does not lend itself to reproducible measurement, in which circumstance, the next largest lesion that can be measured reproducibly should be selected.

Lymph nodes merit special mention since they are normal anatomical structures that may be visible by imaging even if not involved by tumor. As noted above, pathological nodes that are defined as measurable and may be identified as target lesions must meet the criterion of a short axis of ≥ 15 mm by CT scan. Only the short axis of these nodes will contribute to the baseline sum. The short axis of the node is the diameter normally used by radiologists to judge if a node is involved by solid tumor. Nodal size is normally reported as two dimensions in the plane in which the image is obtained (for CT, this is almost always the axial plane; for MRI, the plane of acquisition may be axial, sagittal, or coronal). The smaller of these measures is the short axis. For example, an abdominal node that is reported as being 20 mm x 30 mm has a short axis of 20 mm and qualifies as a malignant, measurable node. In this example, 20 mm should be recorded as the node measurement. All other pathological nodes (those with short axis ≥ 10 mm but < 15 mm) should be considered non-target lesions. Nodes that have a short axis of < 10 mm are considered non-pathological and should not be recorded or followed. Lesions irradiated within 3 weeks prior to Cycle 1, Day 1 may not be counted as target lesions.

Non-Target Lesions

All other lesions (or sites of disease), including pathological lymph nodes, should be identified as non-target lesions and should also be recorded at baseline. Measurements are not required.

It is possible to record multiple non-target lesions involving the same organ as a single item on the Case Report Form (CRF) (e.g., "multiple enlarged pelvic lymph nodes" or "multiple liver metastases").

After baseline, changes in non-target lesions will contribute only in the assessment of complete response (i.e., a complete response is attained only with the complete disappearance of all tumor lesions, including non-target lesions) and will not be used to assess progressive disease.

New Lesions

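### Section 8.3.2 codes metastatic burden as fewer than 5 versus 5 or more sites without giving a reason, and leaves the coding of the Cox term unclear; a numeric or ordinal count would usually use the data better

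*Protocol*

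**What the plan says.** Section 8.3.2 (Efficacy Analysis) plans one analysis of metastatic burden: "Secondary analysis will investigate the impact of the number of metastatic sites in 2 modalities (<5 and ≥5"). It continues: "A semi-parametric Cox model stratified on the cohort and adjusted for the number of metastasis will be developed". The first sentence counts sites and the second counts metastases. The second gives no cut-point and no functional form. Neither gives a reason for cutting at 5.

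Other parts of the protocol bear on this:

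- Section 4.1 requires one measurable metastasis suitable for SABR and, in addition, "one not treated measurable metastasis by RECIST 1.1. If all tumour sites are accessible to SABR, one of them will not be treated". Every patient therefore has at least two metastases.
- Section 8.3.1 leaves further work open: "Exploratory analyses of the data not described below will be conducted as deemed appropriate".
- Appendix 4 limits target lesions at baseline: "All measurable lesions up to a maximum of two lesions per organ and five lesions in total". For the rest it says: "All other lesions (or sites of disease) should be identified as non-target lesions and should also be recorded at baseline".
- Appendix 5 (modified RECIST) adds: "It is possible to record multiple non-target lesions involving the same organ as a single item on the Case Report Form (CRF").
- The synopsis describes the trial as "Open-label, non-comparative, phase II clinical trial conducted in four cohorts of patients".

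**The concern.** Number of metastases is the only prognostic factor for PFS that the protocol names, and the only coding it specifies is a split at 5. That coding treats patients with 2, 3 and 4 metastases as alike, and patients with 5 as like those with any larger number. If risk changes gradually with burden, the contrast is less likely to show a real relation, and its hazard ratio depends on a cut that nothing in the protocol supports.

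The Cox sentence does not settle the matter. If its term is the two-level factor, the same loss applies there. If it is the count, the protocol does not say so, and it does not say whether organ sites or individual lesions are counted.

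**Working it through.** **The plan's own figure.** The protocol attaches no effect size, power or event count to this analysis, so there is nothing to reproduce. The effect sizes, distributions and event counts below are assumptions.

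**Events.** Section 8.1 gives 187 patients and a one-year PFS between 15% and 32%. Events by one year are then 187 × 0.68 = 127 to 187 × 0.85 = 159. I use 120 and 150. The share of information lost does not depend on this choice; the power figures do.

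**Information kept, normal covariate.** When the true effect is linear in X, the efficiency of a split relative to the uncut term is the squared correlation between X and the indicator. For a normal X with a proportion p at 5 or more, this is φ(z_p)² / [p(1 − p)].

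| Proportion at 5 or more | Kept | Lost |
|---|---|---|
| 50% | 63.7% (= 2/π) | 36.3% |
| 40% or 60% | 62.2% | 37.8% |
| 30% or 70% | 57.6% | 42.4% |
| 20% or 80% | 49.0% | 51.0% |
| 10% or 90% | 34.2% | 65.8% |

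**Information lost, counts.** The same squared correlation was computed for counts starting at 2 (Poisson and geometric shapes, assumed means 3 to 8). The loss is about 29% to 67% for an effect on the log count, and about 32% to 79% for an effect on the raw count. If risk truly steps at 5, the split loses nothing.

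**Power.** For a hazard ratio HR per SD and D events, power at two-sided 5% is Φ(ln(HR)·√(D·e) − 1.96), where e is the information kept (e = 1 uncut). With D = 150:

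| HR per SD | Uncut | 50/50 split | 70/30 split |
|---|---|---|---|
| 1.15 | 40% | 28% | 25% |
| 1.20 | 61% | 43% | 40% |
| 1.25 | 78% | 59% | 55% |
| 1.30 | 90% | 73% | 68% |

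For example, at HR 1.25, ln(1.25)·√150 = 2.73 and Φ(2.73 − 1.96) = 0.78. With e = 0.637 the first term falls to 2.18 and Φ(0.22) = 0.59. Over 120 or 150 events and both splits, the gain from not cutting runs from 10 points (D = 120, HR 1.15, 50/50: 0.334 versus 0.230) to about 23 points (D = 120, HR 1.30, 70/30: 0.820 versus 0.587).

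**If high counts are capped.** These gains assume a fully observed covariate. For the score 2, 3, 4, 5 or more, take the same normal model and suppose that the group below 5 divides equally among 2, 3 and 4:

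| Proportion at 5 or more | Kept by score | Kept by split | Power gain |
|---|---|---|---|
| 30% | 85% | 58% | 8 to 17 points |
| 50% | 77% | 64% | 4 to 8 points |
| 70% | 62% | 58% | 1 to 3 points |

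With shifted Poisson or geometric counts, a log effect and means of 3 to 5, the score keeps about 83% to 98% and the split 33% to 71%. At means of 6 to 8 the score adds little, because most patients sit at the cap.

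**The case against.** Several stronger readings are tempting, and the documents do not support them.

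- *Burden is studied only as a split.* The Cox sentence names the number of metastases with no cut, and a plain reading could be the count. Section 8.3.1 also leaves exploratory analyses open. What stands is that the split is the only coding specified.
- *The trial must already hold the exact count.* Sorting patients at 5 requires counting only up to 5. Target lesions are capped at five, and Appendix 5 lets several non-target lesions in one organ be entered as a single item. Exact high counts may not exist.
- *The Cox adjustment is left incomplete.* The trial is non-comparative and the model names no other covariate, so there is no treatment contrast for residual burden to confound.
- *More than a third of the information is lost, as a fact.* That needs a roughly normal burden and a linear effect, and the documents give neither. Under a true step at 5 the loss is zero, and a numeric term would then be the less efficient choice.

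It is also fair to say that the form of a covariate is commonly left to the SAP, which is not at hand. That answers the silence about the Cox term. It does not answer the two-level coding, which the protocol itself fixes. Nor is the possibility of later exploratory work a substitute for a prespecified form. Finally, this analysis carries no hypothesis or error rate, and no decision in the protocol depends on it. That limits the weight of the point but does not remove it.

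**Conclusion.** The point holds as a minor improvement to a secondary analysis. Section 8.3.2 fixes an unexplained split, mixes sites and metastases, and does not say how the Cox term is coded. If burden acts gradually, the split costs roughly 30% or more of the information. In the illustrated normal-covariate cases, a fully observed numeric term would recover 10 to 23 points of power. These figures rest on assumed distributions, effect sizes and event counts. The loss is zero under a true threshold at 5, and the recoverable part shrinks to 1 to 3 points if counts are capped and 70% of patients have 5 or more. The primary per-cohort binomial test is not touched.

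**What to change.** In section 8.3.2 (or the SAP, if the protocol refers to it):

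1. Define one unit, organ sites or individual lesions, and use it in both sentences.
2. Enter the baseline count in the cohort-stratified Cox model as a numeric term: the log of the count, or a spline if the relation is non-linear. With the log, report the hazard ratio per doubling.
3. Where high counts are grouped on the CRF, use the ordinal score 2, 3, 4, 5 or more. If the unit chosen is organ sites, the score would need to start at 1, since two metastases can lie in one organ.
4. Keep the Kaplan-Meier curves for fewer than 5 versus 5 or more as a descriptive display, so that a step at 5 would still be seen.

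This takes a sentence or two and no extra patients. The price is a shape assumption and a less immediate summary than a two-group contrast, for a gain that may be small if most patients are at the cap.

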8.3.3 Safety Analysis

All included subjects who take at least 1 dose of the atezolizumab will be included in the safety analyses. Adverse events will be summarized by worst severity grade. AEs, as well as treatment-emergent AEs, will be summarized by system organ class, and preferred term. Atezolizumab-related adverse events, adverse events leading to death or to discontinuation from treatment, events classified as NCI-CTCAE v4.0 Grade 3 or Grade 4 (or moderate/severe if other rating scale is used), atezolizumab-related events, and serious adverse events will be summarized separately.

Cross tabulations will be provided to summarize frequencies of abnormalities.

By-subject listings will be provided for all relevant safety data.

Graphical displays and figures will be provided where useful to assist in the interpretation of results especially blood pressure handling.

Descriptive analysis will be described for:

- Deaths,
- SAEs.
- AE drop-outs,
- AEs.

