ventilation)	 Consider anti-cytokine therapy. For patients who are refractory to anti-cytokine therapy, experimental treatments f may be considered at the discretion of the investigator and in consultation with the Medical Monitor.
	Hospitalize patient until complete resolution of symptoms.

ASTCT=American Society for Transplantation and Cellular Therapy; BiPAP=bi-level positive airway pressure; CAR=chimeric antigen receptor; CPAP=continuous positive airway pressure; CRS=cytokine-release syndrome; CTCAE=Common Terminology Criteria for Adverse Events; eCRF=electronic Case Report Form; HLH=hemophagocytic lymphohistiocytosis; ICU=intensive care unit; MAS=macrophage activation syndrome; NCCN=National Cancer Comprehensive Network; NCI=National Cancer Institute.

The management guidelines have been adapted from NCCN guidelines for management of CAR T-cell–related toxicities (Version 2.2019).

- ^a Grading system for management guidelines is based on the ASTCT CRS consensus grading scale. NCI CTCAE V5 and the ASTCT CRS consensus grading scale should be used when reporting severity of CRS on the Adverse Event eCRF. NCI CTCAE V5 should be used when reporting severity of organ toxicities associated with CRS on the dedicated Cytokine Release Syndrome eCRF. Organ toxicities associated with CRS should not influence overall CRS grading.
- b Fever is defined as temperature ≥ 38°C not attributable to any other cause. In patients who develop CRS and then receive anti-pyretic, anti-cytokine, or corticosteroid therapy, fever is no longer required when subsequently determining event severity (grade). In this case, the grade is driven by the presence of hypotension and/or hypoxia.
- Symptomatic treatment may include oral or IV antihistamines, anti-pyretics, analgesics, bronchodilators, and/or oxygen. For bronchospasm, urticaria, or dyspnea, additional treatment may be administered as per institutional practice.
- d Low flow is defined as oxygen delivered at ≤ 6 L/min, and high flow is defined as oxygen delivered at > 6 L/min.

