9.1.5 Intensity criteria

Intensity criteria must not be confused with criteria for seriousness, which serve as guidelines for definition of reporting obligations.

Intensity of events will be estimated according to the NCI-CTCAE classification, version 4.0 (toxicity score grade 1 to 5). Intensity of adverse events not listed in this classification will be evaluated according to the following terms:

- Mild (grade 1): does not affect the patient's usual daily activity
- Moderate (grade 2): perturbs the patient's usual daily activity
- Severe (grade 3): prevents the patient carrying out his usual daily activities
- Very Severe (grade 4): necessitates intensive care or is life-threatening
- Death (grade 5)

9.2 Reporting of Serious Adverse Events (SAE), Adverse Events of Special interest (AESI) and pregnancy

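### Section 8.3.3 equates moderate/severe with grade 3 or 4, but the protocol's own verbal scale in section 9.1.5 makes those words grades 2 and 3 (minor; wrong as written)

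*Protocol*

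**What the plan says.** Protocol section 8.3.3 (Safety Analysis) lists several safety outputs. Adverse events are summarised by worst severity grade, and by system organ class and preferred term. Certain groups of events are then summarised separately, among them "events classified as NCI-CTCAE v4.0 Grade 3 or Grade 4 (or moderate/severe if other rating scale is used"). The section does not name the other rating scale.

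Protocol section 9.1.5 (Intensity criteria) grades events with CTCAE on a 1 to 5 score and adds a verbal scale for the rest: "Intensity of adverse events not listed in this classification will be evaluated according to the following terms". Three steps of that scale matter here:

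- "Moderate (grade 2): perturbs the patient's usual daily activity"
- "Severe (grade 3"), an event that prevents usual daily activities
- "Very Severe (grade 4): necessitates intensive care or is life-threatening"

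Mild is grade 1 and death is grade 5.

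**The concern.** The parenthesis in 8.3.3 is meant to say which events, when graded by some scale other than CTCAE, belong with CTCAE grades 3 and 4. The words it uses do not have that meaning in 9.1.5. A summary built on it would combine CTCAE grades 3 and 4 with a different pair of grades for unlisted events, so one count would carry two definitions of high grade.

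What is at stake is the consistency of one descriptive safety table. Toxicity is a stated secondary objective (section 2.2), and a statistician who follows 8.3.3 to the letter would carry the mismatch into the report.

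**Working it through.** The protocol states no figure to reproduce. The check sets the two sections side by side.

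**Inputs**

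- Target category: CTCAE grades {3, 4} (section 8.3.3).
- Words chosen for another scale: moderate and severe (section 8.3.3).
- Meaning of the words: mild = 1, moderate = 2, severe = 3, very severe = 4, death = 5 (section 9.1.5).

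**Mapping**

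| Term in 9.1.5 | Grade | In the intended category {3, 4}? | Selected by moderate/severe, taken literally? |
|---|---|---|---|
| Mild | 1 | no | no |
| Moderate | 2 | no | yes |
| Severe | 3 | yes | yes |
| Very severe | 4 | yes | no |
| Death | 5 | no | no |

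The rule selects {2, 3} and the target is {3, 4}. Only grade 3 is common to both. Grade 2 is wrongly included and grade 4 is wrongly omitted. Grade 5 lies outside both sets, but 8.3.3 covers deaths and events leading to death separately.

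**A looser reading.** If severe is taken to include very severe, the rule selects {2, 3, 4}. Grade 4 is recovered, but grade 2 is still wrongly included.

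**Size.** Let m, s and v be the numbers of unlisted events that are moderate, severe and very severe.

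- Literal rule: m + s
- Looser reading: m + s + v
- Consistent with 9.1.5: s + v

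The error in the count is (m + s) − (s + v) = m − v under the literal rule, and (m + s + v) − (s + v) = m under the looser one. The protocol gives none of these numbers, so the error cannot be quantified. Where m = v the literal total would happen to be right while the events in it were still wrong.

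**Does another scale explain the wording?** The other non-CTCAE scale in the protocol is the one for cytokine-release syndrome in section 5.3.2.7: "NCI CTCAE V5 and the ASTCT CRS consensus grading scale should be used when reporting severity of CRS on the Adverse Event eCRF". It is set out there as grades 1 to 4, without the words moderate or severe, so it cannot be the source of the parenthesis. That leaves 9.1.5 as the only verbal scale the phrase could refer to.

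**The case against.** The strongest reply is that 8.3.3 never cites 9.1.5. The 9.1.5 scale attaches a number to every word, on the same 1 to 5 range as CTCAE. Unlisted events could therefore enter the high-grade summary by their number, with the parenthesis only a general fallback for a scale that has no numbers. On that reading no event is misplaced. The reading is possible, but it leaves the parenthesis with no scale in the protocol to refer to, and 8.3.3 ties the numeric route to CTCAE grades by name. Under no scale in the protocol does moderate mean grade 3 or 4.

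A second reply is that nobody building a high-grade table would take severe events and leave out very severe ones. That has force. The omission of grade 4 depends on a strictly literal reading and is the weaker half of the point. The inclusion of grade 2 does not depend on it.

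A third reply is that little is lost, and this stands. Section 8.3.3 also provides a worst-grade summary, by-subject listings and a summary of serious adverse events. A life-threatening event is serious by the definition in section 9.1.2. The stopping rule in section 8.2 has its own criterion of grade 4 and above and does not use the 8.3.3 phrase.

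**Conclusion.** The phrase in 8.3.3 is wrong as written. Applied to the scale in 9.1.5, it brings unlisted grade 2 events into the high-grade summary and, read literally, leaves unlisted grade 4 events out. This rests on one inference: that the unnamed other scale is the one in 9.1.5, the only verbal scale for adverse events in the protocol.

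The correction is minor. It concerns only events not listed in CTCAE, probably few, and one descriptive summary. The primary endpoint, sample size, decision thresholds, stopping rule and reporting of serious events are untouched.

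A reader might infer three stronger things that the protocol does not support:

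- That the trial's principal toxicity result is compromised. Section 8.3.3 lists the grade 3 or 4 summary as one of several and does not rank it first.
- That the high-grade count would be inflated by some stated multiple. Any such multiple needs an assumed mix of unlisted events, and would apply to those events alone and not to the whole table, which also holds every CTCAE-graded event.
- That life-threatening events would vanish from the report. They remain in the other outputs.

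**What to change.** In section 8.3.3, replace the parenthesis after the CTCAE grades with: (or severe/very severe on the scale of section 9.1.5 for events not listed in CTCAE). This names the scale and makes its words match grades 3 and 4. Any statistical analysis plan that repeats the present phrase should carry the same change.

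The cost is one phrase. No new data are needed, and neither the grading of events nor patient management changes.
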